6.4 Withdrawal of individual subjects

Subjects can leave the study at any time for any reason if they wish to do so without any consequences. The investigator can decide to withdraw a subject from the study for urgent medical reasons.

6.5 Replacement of individual subjects after withdrawal

None. We will run intention-to-treat analyses.

6.6 Follow-up of subjects withdrawn from treatment

Yes, if the participant is willing to do the assessments.

6.7 Premature termination of the study

The researchers did not identify criteria for premature termination. The interventions that are tested have been found to be feasible and safe in this population and the study is situated in routine clinical practice. Premature termination of the study is not probable.

7. SAFETY REPORTING

7.1 Temporary halt for reasons of subject safety

In accordance to section 10, subsection 4, of the WMO, the investigator will suspend the study if there is sufficient ground that continuation of the study will jeopardise subject health or safety. The investigator will notify the accredited METC without undue delay of a temporary halt including the reason for such an action. The study will be suspended pending a further positive decision by the accredited METC. The investigator will take care that all subjects are kept informed.

7.2 AEs, SAEs and SUSARs

7.2.1 Adverse events (AEs)

Adverse events are defined as any undesirable experience occurring to a subject during the study, whether or not considered related to the trial procedure or experimental intervention. All adverse events reported spontaneously by the subject or observed by the investigator or his staff will be recorded.

7.2.2 Serious adverse events (SAEs)

A serious adverse event is any untoward medical occurrence or effect that

- results in death;
- is life threatening (at the time of the event);
- requires hospitalisation or prolongation of existing inpatients' hospitalisation;
- results in persistent or significant disability or incapacity; or
- any other important medical event that did not result in any of the outcomes listed above due to medical or surgical intervention but could have been based upon appropriate judgement by the investigator.

An elective hospital admission will not be considered as a serious adverse event.

If a SAE occurs, the responsible clinician/ specialist is responsible for the treatment plan and resulting actions. The principle investigator will report the SAEs through the web portal *ToetsingOnline* to the accredited METC that approved the protocol within 7 days of first knowledge for SAEs that result in death or are life threatening followed by a period of maximum of 8 days to complete the initial preliminary report. All other

Version number: 2.0, date 15-02-2019

SAEs will be reported within a period of maximum 15 days after the investigator has first knowledge of the serious adverse events.

8. STATISTICAL ANALYSIS

The primary and secondary outcomes will all be analysed intention-to-treat. We will run completers (sensitivity) analyses to test the robustness of our findings. Both the primary and secondary continuous outcomes will be analysed with Linear Mixed Models (LMM) with baseline values added as covariates. Dichotomous primary and secondary outcomes will be analysed with Generalized Estimating Equations (GEE). The main outcome will be the effect over time. We will also compute the effects for the different time-points using interaction terms. The predictive value of the potential predictor variables will be tested with regression analyses. To test whether the effects of PE, EMDR and CR on the primary and secondary outcomes endure on the long term, we will test the changes between the 6-month follow-up and the 12-month and 24-month follow-up respectively. These within group changes will be analysed with paired samples t-tests (continuous outcomes) and McNemar's tests (dichotomous outcomes). We will also test for differences between PE, EMDR and CR at these time points with independent samples t-tests and Chi-square tests for independence.

We will apply explorative multilevel network models to study the dynamics of post-traumatic stress and psychosis factors using the daily assessments at baseline and post-treatment. The variables in these assessments will be standardized to enhance comparability of the coefficients.⁷⁷ We will estimate a multilevel vector-autoregressive model that produces three networks: a temporal within-person network (lagged associations), a contemporaneous networks (within-time-window associations), and a between-person network (variance-covariance structures of mean scores).⁷⁸⁻⁸⁰ These analyses will shed light on how post-traumatic stress and psychosis factors interact over time and how active intervention influences these interactions. They will also identify factors with high 'out-strength' (factors that have the highest influence on variables at the next time-point) and high 'in-strength' (factors that are influenced the most by variables at the previous time-point).

If a treatment is found to be effective, cost-effectiveness analyses will be performed. The incremental cost-effectiveness ratios (ICERs) are considered to be a single-point estimate of an underlying continuum. Acceptability curves are produced with bootstrap simulations and confidence intervals. The outcome will be costs in Euro's per QALY and the costs in Euro's per day without PTSD gained. If none of the treatments are effective, which is not expected, a cost-minimization calculation will be performed. Inductive

Thematic Analysis will be used to analyse themes in the views of participants TFT and the process of recovery.^{81,82}

The trial is deemed successful when we have included enough participants to carry out all above-mentioned analyses and answer all hypotheses.

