4.4 Sample size calculation

Sample size for longitudinal intention-to-treat (ITT) analyses with linear mixed models (LMM) was calculated according to the method presented by Liu and Liang $(1997)^{45}$ and based on data from previous RCTs.^{21,40} Although an ITT analysis with LMM is robust against moderate attrition, we aim to include an additional 20% to compensate for dropout. With alpha = 0.05; beta = 0.2; rho = 0.45; 3 repeated follow-up assessments; we will need 50 participants in each arm to detect at least medium effects (0.5), which are expected based on previous research. Therefore, we aim to include 200 participants.

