6.1.3 Other study parameters (if applicable)

12-month and 24-month follow-up outcomes for the primary and secondary study parameters in the PE, EMDR and CR conditions. Since the WL group is not assessed at 12 and 24-month follow-up, these comparisons are within group, i.e. 12 and 24-month follow-up outcomes are compared with the 6-month follow-up data for each arm. Cost-effectiveness of PE, EMDR and CR compared to WL between baseline and 6-month follow-up. Potential baseline predictors are PTSD, complex PTSD, paranoid ideation, negative impact of voices and social support. The baseline and post-treatment assessment will be augmented by daily monitoring to study how post-traumatic stress and psychosis symptoms dynamically interact and how treatment affects these dynamic interactions (see daily monitoring below).

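### The 12- and 24-month outcomes leave the mixed model for stand-alone tests that are less precise, more exposed to dropout, and cannot by themselves support a claim that effects last

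*Protocol*

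**What the plan says.** Section 8 analyses the primary and secondary outcomes by intention to treat, with baseline-adjusted LMM for continuous and GEE for dichotomous outcomes. Completers analyses are a sensitivity check. Section 4.4 describes intention-to-treat LMM as able to withstand moderate loss to follow-up.

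For the longer term, section 8 asks whether the effects of PE, EMDR and CR last, and compares 6 months with 12 and with 24 months. It fixes the tests by name: "These within group changes will be analysed with paired samples t-tests (continuous outcomes) and McNemar's tests (dichotomous outcomes". It then adds: "We will also test for differences between PE, EMDR and CR at these time points with independent samples t-tests and Chi-square tests for independence". It gives no covariate, missing-data approach or maintenance margin for these tests.

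Section 6.1.3 lists the 12- and 24-month outcomes under other study parameters and explains: "Since the WL group is not assessed at 12 and 24-month follow-up, these comparisons are within group". Section 2 makes long-term effects the third objective. It also names PE and EMDR against CR as one of the two comparisons of main interest.

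**The concern.** A paired t-test or McNemar's test uses only people seen at both visits. An independent t-test or chi-square test uses only people seen at that visit. None of them draws on baseline or on intermediate visits. At 12 and 24 months the analysis thus gives up the features for which the LMM was chosen.

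The loss matters most for PE, EMDR and CR. These arms remain a randomised comparison up to 24 months, and the absence of the waiting list after 6 months does not stop the model from being extended to them.

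The within-arm part has a second weakness. The question is whether effects endure, but the tool is a test of no change, with no margin and only moderate power. A non-significant result would be compatible both with maintenance and with a relevant relapse.

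**Working it through.** **Inputs.** Section 4.4 gives the design values: "With alpha = 0.05; beta = 0.2; rho = 0.45; 3 repeated follow-up assessments". The target is a standardised difference of 0.5 with 50 per arm (200 in total), and this total already contains a 20% allowance for dropout.

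**Assumptions, not stated in the protocol for these visits:** two-sided tests; SD = 1; 40 of 50 per arm observed at 12 or 24 months (the 20% dropout allowance carried forward); correlation 0.45 between 6 and 24 months and between baseline and the late visits. The correlation is varied below.

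**1. The plan's own sample size.** For a mean over m = 3 follow-ups with exchangeable correlation:

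n = 2(z₀.₉₇₅ + z₀.₈)² × [1 + (m − 1)ρ] / (m d²) = 2 × 7.849 × 1.9 / (3 × 0.25) = 39.77, so 40 per arm.

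Then 40 / 0.8 = 50 per arm, and 4 × 50 = 200. This reproduces the plan exactly, and the sample size is not in dispute. The 80% power belongs to an analysis that pools three follow-ups. It does not carry over to a t-test at a single visit.

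**2. Between arms at one late visit, 40 per arm.**

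- Unadjusted: detectable d = 2.80 × √(2/40) = 0.626.
- Baseline-adjusted, ρ = 0.45: 2.80 × √(2 × (1 − 0.45²)/40) = 2.80 × √(2 × 0.7975/40) = 0.559.
- The unadjusted variance is 1/0.7975 = 1.25 times the adjusted one.
- If the baseline correlation is 0.3, the adjusted figure is 2.80 × √(2 × 0.91/40) = 0.597. If it is 0.6, it is 2.80 × √(2 × 0.64/40) = 0.501.
- Power at d = 0.5 is 60% unadjusted (noncentral t; 61% by normal approximation) against 71% adjusted (normal approximation, ρ = 0.45). With all 50 per arm it is 70% against 80%.

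**3. Within arm, 6 months against a later visit, 40 pairs.** The SD of the change is √(2(1 − ρ)), which is 1.049 at ρ = 0.45. The paired t-test has 80% power at a standardised change of 0.454, that is, at a loss of 0.454 × 1.049 = 0.476 SD. At ρ = 0.6 this is 0.454 × √0.8 = 0.41 SD, and at ρ = 0.7 it is 0.454 × √0.6 = 0.35 SD.

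| True loss (SD) | Power, ρ = 0.45 | Power, ρ = 0.6 | Power, ρ = 0.7 |
|---|---|---|---|
| 0.2 | 22% | 28% | 36% |
| 0.3 | 42% | 54% | 67% |
| 0.4 | 65% | 79% | 89% |
| 0.5 | 84% | 93% | 98% |
| 95% CI half-width (SD) | 0.335 | 0.286 | 0.248 |

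A true loss of 0.3 SD would be non-significant 58%, 46% or 33% of the time.

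**4. Selective dropout.** A simulation took no true mean change after 6 months and ρ = 0.45. Dropout was 20% to 30%, and more likely with a higher 6-month score (assumed log-odds 0.5 to 1.0 per SD). The complete-pair change was biased by +0.05 to +0.14 SD, and the mean of those seen at 24 months by −0.04 to −0.11 SD. On a symptom scale the first is spurious worsening and the second a flattering late level. Size and direction depend on the assumed mechanism. An LMM that includes the 6-month score uses the information on which this dropout depends.

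**The case against.** **The intention-to-treat statement.** A reader might infer that the late tests flatly breach it. The text does not clearly support that. The statement covers primary and secondary outcomes, which sections 6.1.1 and 6.1.2 define as changes up to 6 months, and section 6.1.3 puts the later visits in a lower tier. What stands is that a weaker method was chosen for a named objective when a better one was already in the plan.

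**The reading of non-significance.** A reader might infer that a real loss of benefit would be reported as lasting benefit. Section 8 states no such rule; it says only that the changes will be tested. The paired test can also detect larger losses (84% power at 0.5 SD). The point is limited to this: with no margin, a non-significant result is not evidence of maintenance.

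**Direction of bias and attrition.** In the simulated scenario the paired test is pushed towards showing worsening, which works against a claim of lasting effect. The protocol gives no attrition by visit, so heavier loss at 24 months is plausible but not documented.

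**Number of tests.** Multiplying 16 named outcomes by 2 visits and 3 arms or pairs suggests 96 tests per family. The documents do not support that count, because social functioning, adversities and revictimization are scheduled for weekly monitoring only up to 6 months. Thirteen outcomes would give 13 × 2 × 3 = 78, and the figure shifts again with how scales are counted. Nothing here rests on it.

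**Sections 6.1.3 and 8.** The first speaks of within-group comparisons and explains this by the missing waiting list; the second adds tests between active arms. This is an addition to be acknowledged, not a serious contradiction.

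**The unseen SAP.** It may add missing-data detail. The protocol nevertheless names the tests, so the choice has not simply been left open.

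**Conclusion.** The point holds as a limited one about the third objective. The named tests drop participants missing the relevant visit or visits and discard baseline and intermediate data, although the existing model could carry PE, EMDR and CR to 24 months. Between arms, the cost is a detectable difference of about 0.63 SD instead of 0.56 SD (0.50 to 0.60 for baseline correlations of 0.6 down to 0.3). Within arm, power for a 0.3 SD loss is about 42%, or 54% to 67% with a higher correlation. All these figures assume 40 observed per arm.

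With complete data, the model would not make the within-arm change much more precise. Its benefit there is better handling of incomplete follow-up, together with an estimate and interval that show what has and has not been excluded. The change is worth making.

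**What to change.** - In section 8, extend the LMM to 12 and 24 months in PE, EMDR and CR, with baseline as covariate. Everyone randomised to those arms should contribute whatever follow-up they have.
- For dichotomous outcomes, extend the GEE or use a likelihood-based binary model, and state how missing data are handled. Ordinary GEE is less robust to selective dropout.
- Take the between-arm contrasts at 12 and 24 months, and the changes from 6 to 12 and from 6 to 24 months, from this model with 95% CIs. Replace the stand-alone tests, or keep them only as completers sensitivity analyses.
- State that a non-significant change will not be read as maintenance. If maintenance is to be claimed, set a margin in advance, at least for the CAPS. Margins for every outcome are optional. With a CI half-width of about 0.25 to 0.34 SD, a small margin would usually not be met.
- Add a line to section 6.1.3 acknowledging the comparisons between active arms.

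The cost is slightly more modelling work and, if maintenance is to be claimed, agreement on a margin. No new data are needed. Lasting effect becomes harder to claim.

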9. ETHICAL CONSIDERATIONS

9.1 Regulation statement

The study will be conducted according to the principles of the Declaration of Helsinki (October 2013) and in accordance with the Medical Research Involving Human Subjects Act (WMO).

9.2 Recruitment and consent

Patients will be referred to the study by clinicians from the participating centres. After both oral and written presentation of information about the study, and at least one-week time to decide upon participation, the patient is asked to sign informed consent.

9.3 Objection by minors or incapacitated subjects (if applicable)

Subjects will be capacitated and competent adults. In the informed consent, it will be stated clearly that participation in the study and associated interventions is voluntary in any case.

9.4 Benefits and risks assessment, group relatedness

The participants will probably benefit from the given therapy. Worsening of symptoms or other adverse events as a result of the interventions are not expected, as previous research has shown that treatment actually significantly reduces the odds of adverse events.

9.5 Compensation for injury

Exemption of risk assurance is asked from the METC because no risks are associated with the present study. We will test evidence-based trauma-focused treatments that are delivered in routine clinical practice, have been found to be safe in patients with psychosis, ^{21,22,40} and which are recommended by the 'zorgstandaard psychose' (www.ggzstandaarden.nl).

9.6 Incentives (if applicable)

Each participant is compensated for traveling expenses with Euro 20 per assessment (total is Euro 120 since there are 6 assessments) plus 50 euros for the daily and weekly assessments. Of course, also participants that prematurely stop their participation will have their compensation for the assessments they attended.

10. ADMINISTRATIVE ASPECTS, MONITORING AND PUBLICATION

10.1 Handling and storage of data and documents

The handling of personal data will comply with the Dutch General Data Protection Regulation. Data will be handled confidentially and data files will be separated from the name, date of birth and address data. The name and data files contain a code for the patient. The code is a two-digit site number and a three-digit patient number (XX-YYY). The principal investigators are the only persons who have the key of this code and have access to the source data. The CASTOR trial management software will be used for this trial. Raw data will be kept for five years according to the NFU guidelines.

10.2 Amendments

Amendments are changes made to the research after a favourable opinion by the accredited METC has been given. All amendments will be notified to the METC that gave a favourable opinion.

10.3 Annual progress report

The investigator will submit a summary of the progress of the trial to the accredited METC once a year. Information will be provided on the numbers of subjects included and numbers of subjects that have completed the trial, serious adverse events/ serious adverse reactions, other problems, and amendments. The METC will be informed about the start of the study (based on the data of inclusion of the first subject) within one month.

10.4 Temporary halt and (prematurely) end of study report

The investigator will notify the accredited METC of the end of the study within a period of 8 weeks. The end of the study is defined as the last patient's last visit.

The sponsor will notify the METC immediately of a temporary halt of the study, including the reason of such an action.

In case the study is ended prematurely, the sponsor will notify the accredited METC within 15 days, including the reasons for the premature termination.

Version number: 2.0, date 15-02-2019

Within one year after the end of the study, the investigator will submit a final study report with the results of the study, including any publications/abstracts of the study, to the accredited METC.

10.5 Public disclosure and publication policy

The trial will be registered at an international trial register. The results on all hypotheses will be published, unreservedly, in the way this document has described. The sponsor will have no influence on the publication of the results.

12. APPENDICES

Appendix 1: Research Plan and Timeline

Item	Timeline
Recruiting therapists/ sites and PhD students	May – September 2018
Finalizing protocol	≤ September 2018
Training therapists	September 2018 – February 2019
Science committee APH	October – December 2018
Medical Ethics Review Board	December 2018 – February 2019
Online registry	February 2019
Team trainings	February – July 2019
Recruiting research assistants	October – December 2018
Start inclusion	1 st of March 2019
End of inclusion	December 2021
Last post-treatment assessment	April 2022
Last 6-month follow-up assessment	October 2022
Last 24-month follow-up assessment	April 2023
Data analyses and writing manuscripts	≥ December 2021

Appendix 3: Budget

	Participating	Funding body
	organizations	Stichting Tot
Costs	(matching)	Steun VCVGZ
Coordination and management of the trial, principal investigator	€240.000,-	
and data monitor: 5yrs*0.60fte*€80.000,-=		
Supervising the PhD student by professor and co-promotor:	€50.000,-	
5yrs*0.11fte*€90.000,-=		
Productivity loss therapists for training: 24therapists*8dys*€882,-	€169.334,-	
Productivity loss therapists for supervision: 24therapists*12sessions*3yrs*€441,-=	€381.024,-	
Supervising the therapists: 3yrs*12sessions*3supervisors*€441,-=	€47.628,-	
Per diem for expert by experience in trial management team:		€4.800,-
20meetings*€300,-=		
Costs of training therapists in PE/EMDR and in CR (on average		€18.000,-
8 days of training per therapist):		
Accommodation for the training of therapists (including travel		€10.300,-
and hotel UK trainer):		
8dys*€1.200,-=€9.600,- 2days*€350,-return flight+2 nights hotel=€700,-		
Accommodation for supervising of therapists (including travel		€31.500,-
and hotel UK supervisor):		
3yrs*12sessions*€446,-accomodation costs=€16.056,-		
3yrs*12sessions*€250,-return flight+1 night hotel=€9.000,-		
Training teams in trauma-sensitive attitude and screening. The		€16.000,-
training is delivered by an expert in trauma and psychosis and		
an expert with lived experience of both trauma and psychosis:		
8trainings*€2.000,-=		
Productivity loss for training teams in trauma-sensitive attitude and screening: 48teams*8participants per team*€882,-=	€338.688,-	
Treatment delivered: 180 participants*18treatments*€196,-=	€635.040,-	
0.80 fte PhD student, for assessments and supervising research		€220.000,-
assistants: 5yrs*€55.000,-*0.80fte=		
Internship fee for research assistants to do assessments:		€8.400,-
3yrs*8ra's*€350,-=		
Compensation for expenses by participants/ incentives:		€34.800,-
(136participants*7assessments*€20,-)+(30part*5assess*€20,-)+(166part*€60,-)=		
Travel expenses:	€12.500,-	
Daily monitoring application:		€20.000,-
Smartphones for daily assessment: 80*€200,-=		€16.000,-
Diverse costs and unforeseen costs:		€15.000,-
Total costs over 5 years	€1.874.214,-	€394.800,-

Appendix 4: Planned publications

- 1) Protocol paper
- 2) Primary and secondary outcomes
- 3) Objective effects on symptom worsening, adversities, and revictimization
- 4) Subjective expectancies and experiences of participants (incl burden, harm, effects)
- 5) Cost-effectiveness (6, 12 and 24 mo fu)
- 6) Long-term primary and secondary outcomes (12 and 24 mo fu)
- 7) How do trauma-related psychological mechanisms interact with psychosis (before and after therapy)?
- 8) Does memory contextualization predict severity of re-experiencing symptoms and auditory hallucinations psychosis (baseline data)?
- 9) How do trauma-related psychological mechanisms and PTSD symptoms interact over the course of therapy?
- 10) Predictors/moderators of treatment response (symptoms) and recovery.
- 11) Qualitative analysis of experiencing TFT and the recovery process

Version number: 2.0, date 15-02-2019
